12.1.5 Suspected Unexpected Serious Adverse Reaction

A suspected unexpected serious adverse reaction (SUSAR) is an AE that is assessed as serious, related and unexpected.

12.2 Reporting of Adverse Events

All study subjects will be carefully monitored for the occurrence of AEs during the study period from the informed consent signatory to the completion of the follow-up visit (30 days after the last IMP dose). AEs will be daily recorded by the subject in the subject diary.

Clearly related signs, symptoms and abnormal diagnostic procedure results should be grouped together and reported as a single diagnosis or syndrome whenever possible.

All AEs including but not limited to events reported by the subject, or reported in answer to an open question by the Investigator or member of this team, which fall into any of the above definitions must be recorded as an AE in the eCRF and should include the following information:

- Brief description of the event (diagnosis)
- Start date (and time, if relevant)
- Stop date (and time, if relevant) (or resolution)
- Severity
- Action taken regarding study drug
- Opinion on causality
- Seriousness
- Outcome

Severity

Severity describes the intensity of an event, and will be assessed as:

Mild

The AE does not interfere in a significant manner with the subject's normal functioning level. It may be an annoyance.

Moderate

The AE produces some impairment of function but not hazardous to health. It is uncomfortable and/or an embarrassment.

Severe

The AE produces significant impairment of functioning or incapacitation and/or it is a hazard to the subject.

If an AE changes in severity, the worst severity should be reported.

Causality

Causality will be assessed as:

Version: 4.0

Date: 13 December 2023

Sponsor: Atlas Molecular Pharma S.L. Study Code: ATL001-PI-CEP

NCT No.: 05647343

Related to the Study Treatment

Definitely Related: There is clear evidence to suggest a causal relationship, and other possible

contributing factors can be ruled out. The clinical event, including an abnormal laboratory test result, occurs in a plausible time relationship to study treatment administration and cannot be explained by concurrent disease or other drugs or chemicals. The response to withdrawal of the study treatment (dechallenge) should be clinically plausible. The event must be pharmacologically or phenomenologically definitive, with use of a satisfactory rechallenge

procedure if necessary.

Probable: There is evidence to suggest a causal relationship, and the influence of other

factors is unlikely. The clinical event, including an abnormal laboratory test result, occurs within a reasonable time after administration of the study treatment, is unlikely to be attributed to concurrent disease or other drugs or chemicals, and follows a clinically reasonable response on withdrawal (dechallenge). Rechallenge information is not required to fulfill this definition.

Possible: There is some evidence to suggest a causal relationship (e.g., the event

occurred within a reasonable time after administration of the study treatment). However, other factors may have contributed to the event (e.g., the subject's

clinical condition, other concomitant events).

Not Related to the Study Treatment

Unlikely: A clinical event, including an abnormal laboratory test result, whose temporal

relationship to study treatment administration makes a causal relationship improbable (e.g., the event did not occur within a reasonable time after administration of the study treatment) and in which other drugs or chemicals or underlying disease provides plausible explanations (e.g., the subject's

clinical condition, other concomitant treatments).

Not Related: The AE is completely independent of study treatment administration, and/or

evidence exists that the event is definitely related to another etiology. There

must be an alternative, definitive etiology documented by the clinician.

Follow-up of Subjects after Adverse Events

Any AE that is ongoing when the subject is withdrawn from the study should be followed up until the AE is resolved or the Investigator decides that the AE is stable and needs no further follow-up. The date when the Investigator considers one of these outcomes to have occurred for the last ongoing AE for a subject will be considered the last visit for this subject, and the outcome should be recorded in the eCRF.

Abnormal Laboratory Values/Vital Signs

The reporting of abnormalities as both laboratory/vital signs findings and AEs should be avoided.

An asymptomatic abnormal laboratory/vital sign finding should only be reported as an AE if it is clinically significant, if it fulfils the criteria for a SAE or if it causes the subject to discontinue the study.

If an abnormal laboratory/vital sign value is associated with clinical signs and symptoms, the sign/symptom should be reported as an AE and the associated laboratory/vital sign result should be considered additional information.

12.3 Reporting of Serious Adverse Events

The Investigator is responsible for ensuring that all SAEs are reported to the Sponsor immediately, but in any event no later than 24 hours of any site staff becoming aware of the event. Initial reports should be followed as soon as possible by detailed written reports. The initial and follow-up reports should identify subjects by unique code numbers assigned in the study. The subjects' names, personal identification numbers, and/or addresses must not be included. The following information is **mandatory** for the initial report:

- Subject study ID
- Study treatment (blinded, if applicable)
- Start date (time, if relevant) of the study treatment

Version: 4.0

Date: 13 December 2023

Sponsor: Atlas Molecular Pharma S.L. Study Code: ATL001-PI-CEP

NCT No.: 05647343

- Brief description of the event (diagnosis)
- Start date (time, if relevant) of the event
- Seriousness criteria
- Causality assessment

For reported deaths, the Investigator should supply the Sponsor and the IRB (if applicable) with any additional requested information (e.g., autopsy reports and terminal medical reports).

For reporting of severity, causality, follow-up of subjects after SAEs and SAE reporting in conjunction with abnormal laboratory values/vital signs see Section 12.2.

SAE REPORTING CONTACT DETAILS

Name: Pivotal, S.L.U.

E-mail: [contact]

12.4 Reporting of Suspected Unexpected Serious Adverse Reactions

The Sponsor is responsible for informing the RA and IRB of any individual case reports of SAEs that are determined to be reportable by the Sponsor (i.e., SUSARs) in accordance with US legislation. The Investigator will ensure that all relevant information is provided to the Sponsor to allow the Sponsor to meet their obligations to report the SUSAR to the RA and IRB. For a SUSAR that is fatal or life-threatening, this should be reported as soon as possible and not later than 7 days after the Sponsor was first advised, for any other SUSAR this should be within 15 days.

12.5 Adverse Events of Special Interest

AEs of special interest (AESIs) include all gastrointestinal events which have been assessed as related to the study treatment.

12.6 Precautions/Overdose

Considering that the main aim of this Phase I clinical trial is to investigate the safety and tolerability of multiple and increasing doses of ATL-001, the dose which is considered an overdose has not been determined. However, if a subject receives a dose exceeding 100 mL of ATL-001, this will be considered an overdose, and in such case, the information will be collected following the same timeframe and procedures as for a SAE, even if the overdose is not associated to any AE/SAE. No specific treatment is recommended apart from appropriate supportive measures.

12.7 Pregnancy

Female subjects will be instructed to notify the Investigator immediately if they become pregnant during the study. Male subjects will be instructed to notify the Investigator immediately if their partner becomes pregnant. Pregnant subjects will be withdrawn from further study treatment. The subjects will also be instructed to report pregnancies discovered after the last visit, if they believe that conception occurred during their participation in the study.

A pregnancy as such is not an AE, unless there is a possibility that the IMP has interfered with the efficiency of any contraceptive measures. However, the Investigator should report pregnancies according to the procedures and timelines described for reporting of SAEs (Section 12.3). The pregnancy report form should be used instead of the SAE form.

The pregnant subject or partner will be followed until the end of the pregnancy. Any complication during the pregnancy should preferably be reported as an AE or SAE (if it fulfils SAE criteria). The outcome of the pregnancy must be reported on the pregnancy report form. Any spontaneous abortion, stillbirth, birth defect/congenital anomaly, death, or other serious infant condition must be reported and followed up as a SAE.

Version: 4.0

Date: 13 December 2023

Sponsor: Atlas Molecular Pharma S.L. Study Code: ATL001-PI-CEP

NCT No.: 05647343

13. STATISTICAL METHODS AND DETERMINATION OF SAMPLE SIZE

13.1 Statistical and Analytical Plans

A separate statistical analysis plan (SAP), which will provide more details of the statistical analysis outlined below, will be prepared and approved prior to unblinding the study data. No formal statistical hypothesis of the safety or tolerability are to be tested for this study.

13.1.1 Data Sets to be Analyzed

The analysis sets are defined as follows:

- Safety set: All randomized subjects who receive at least one dose of the study medication regardless of if they have or have not completed the study.
- PK set: All randomized subjects who received at least one dose of the study drug medication and have at least one valid PK measurement.

The analysis of safety and tolerability will be based on the Safety set. PK analysis will be based on the PK set.

Definitions

Baseline is defined as the last non-missing measurement before first treatment administration on Day 1.

13.1.2 Statistical Issues

13.1.2.1 Level of Significance, Multiple Comparisons and Multiplicity

Results of statistical analysis will be interpreted descriptively by treatment arm. All statistical models applied will foremost be used as tools for exploring treatment differences between treatment arms rather than formal testing of hypotheses. For this reason, corrections for multiple testing will not be applied in this study and, therefore, confidence intervals (CIs) or p-values indicating statistically significant differences between treatments should be interpreted as suggestive rather than evidence of differences.

13.1.2.2 Adjustment for Covariates

No adjustment for covariates is planned for this study.

13.1.2.3 Handling of Dropouts and Missing Data

No missing value imputation will be done. All analyses will be conducted on observed data.

13.1.3 Summary Statistics

In general, data will be summarized by means of summary statistics. Continuous data will be presented with the number of observations, mean value, standard deviation, minimum, first quartile (Q1), median. third quartile (Q3) and maximum value. Categorical data will be presented as counts and percentages. The data will be presented for each treatment group by visit.

Individual subject data will be listed.

13.1.4 Primary Endpoint Analysis

The primary safety endpoint will be analyzed in the Safety set.

13.1.4.1 Safety

AEs will be coded using the Medical Dictionary for Regulatory Activities (MedDRA). AEs and AESIs will be summarized and presented by treatment group.

The total number of subjects with at least 1 AE and the total number of AEs will be presented.

Version: 4.0

Date: 13 December 2023

Sponsor: Atlas Molecular Pharma S.L. Study Code: ATL001-PI-CEP

NCT No.: 05647343

The number of subjects and the number of AEs will be tabulated by SOC and by preferred term. AEs will also be tabulated versus worst severity and worst relationship to study medication. In summaries of severity and relationship, subjects who report more than one event that are mapped to the same preferred term will be counted only once under the strongest severity and relationship, accordingly.

SAEs will be separately tabulated and listed. The number of AEs leading to discontinuation will also be tabulated.

13.1.4.2 Tolerability

Descriptive statistics will be calculated for the quantitative variables obtained in the vital signs records, ECG, physical examination and laboratory safety tests (hematology, biochemistry and urinalysis).

Vital Signs

Vital signs data will be presented by individual listings with flagging of abnormal values. Vitals signs data will be summarized by visit and treatment group, together with changes from baseline.

Electrocardiogram

Overall interpretation of ECG results (i.e., normal or abnormal) will be summarized. In addition, standard ECG parameters will be summarized by treatment group, together with changes from baseline.

Physical Examination

Physical examination data will be summarized by treatment group.

All abnormal physical findings will be listed.

Laboratory Safety Assessments

For laboratory data (hematology, biochemistry, and urinalysis), summary statistics will be produced for observed values and for changes from baseline to each visit. In addition, the number of abnormal and clinically significant observations will be tabulated for each treatment group by visit. Abnormal values will be flagged in listings.

Shift tables will be created for a subset of laboratory parameters, which will be defined in the SAP. Shift tables will show the number of subjects who changed from below, within or above the reference range at baseline to below, within or above the reference range at each time of assessment.

For laboratory values which are below the limit of quantification, the value corresponding to the limit of quantification will be used when summarizing data.

13.1.5 Secondary Endpoint Analyses

The secondary PK endpoint analysis will be conducted on the PK set.

13.1.5.1 Pharmacokinetic Analysis

ATL-001 plasma concentration data will be listed by treatment, subject and visit/sampling time point. Descriptive summary statistics will be provided by treatment, and visit/sampling time point, including the frequency (n, %) of concentrations below the limit of quantification and reported as zero.

Summary statistics will include mean (arithmetic and geometric), standard deviation, coefficient of variation (arithmetic and geometric), median, minimum, and maximum. An exception to this is t_{max} where median, minimum and maximum will be presented. Concentrations below limit of quantification will be treated as zero in summary statistics and for PK parameter calculations. A geometric mean will not be reported if the data set includes zero values. The PK data of all subjects who received at least one dose of ATL-001 and who have at least one valid PK measurement will be used in the PK set analysis.

A non-compartmental analysis will be used to calculate the PK parameters detailed on Section 11.2. A normalization by dose will be performed in the main PK parameters ($AUC_{(0-t)}$ and C_{max}).

Unassessable subjects for the PK analysis are:

Version: 4.0

Date: 13 December 2023

Sponsor: Atlas Molecular Pharma S.L. Study Code: ATL001-PI-CEP

NCT No.: 05647343

• Subjects who experienced an AE (e.g., vomiting) and took (or not) concomitant medication, if the experienced AE itself and/or the concomitant medication taken, interferes in a relevant manner with his PK results

- Subjects missing more than four samples throughout the study period.
- Excessive deviation between consecutive blood samples collection from scheduled time of sample collection (more than 10% of the time period between consecutive samplings)
- Subjects with lack of any measurable concentration or only very low plasma concentration for drug product*
- Subjects with non-zero baseline concentration > 5% of C_{max}*
- Subjects with less than three quantifiable concentrations*

*Except for these criteria, decision to exclude a subject from the statistical or PK analysis must be made before bioanalysis and has to be properly documented.

More details on the PK parameters, analysis and presentation of study results will be provided in the PK analyses SAP.

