13.3 Procedures for Reporting any Deviation(s) from the Original Statistical Analysis Plan

Any deviation(s) from the original SAP (as described in the study protocol or in the SAP) will be described and justified in a protocol amendment and/or in a revised SAP and/or in the final report, as appropriate.

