14.11 Protocol Deviations

A protocol deviation is any noncompliance with the protocol or GCP requirements. The classification of protocol deviations in major or minor deviations will be mutually agreed between the Sponsor and the responsible contract research organization (CRO) at the start of the study.

A major protocol deviation occurs when the subject, investigator, or Sponsor fails to adhere to significant protocol requirements affecting entry criteria, administration of study treatment, administration of prohibited medication or withdrawal criteria.

Failure to comply with GCP guidelines will also result in a major protocol deviation. The Sponsor will determine if a major protocol deviation will result in withdrawal of a subject.

Deviations to the study protocol will be documented in a Protocol Deviation Log.

The Sponsor or delegate is responsible for immediately reporting serious breaches according to applicable regulations, as well as deviations from the study protocol that substantially affect the integrity or the safety of the subjects or the scientific validity of the study, to the RA/IRB.

Protocol deviations will be reviewed during a meeting before database lock in order to allocate the subjects into the different analysis sets.

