2. INTRODUCTION

The Statistical Analysis Plan (SAP) has been written based on the Clinical Study Protocol (CSP) version 4.0 (13 December 2023).

The purpose of this document is to describe the procedures and the statistical methods to be applied in the data analysis and to ensure that the statistical methodologies that will be used are complete and appropriate to the study objectives.

The focus of this SAP is for the planned primary, secondary, and exploratory analysis at the final analysis in the study.

Pivotal and WuXi will perform the statistical analyses described in the protocol. Result of the analyses described in this SAP will be include in the Clinical Study Report (CSR).

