2.3.5 Study Visits and Procedures

| | Screening period | Treatment period | | | | | | | | | | | | | Follow-up period | | |
|--|-------------------|--------------------|-----------------|-----------------|---------------|------------------|---------------|------------------|---------------|---------------|---------------|---------------|----------------|----------------|---------------------------------|--------------------------------|---------------------------------|
| | Screening visit | Hospital Admission | | | | | | | | | | | | | Hospital discharge ^f | FU-V1 | FU-V2 |
| Day | Day -30 to Day -1 | Baseline (Day 1) | Day 1 and Day 5 | | | | | | | | | | | | Day 2 and Day 6 | 3 days after the last IMP dose | 30 days after the last IMP dose |
| Assessment time | | Pre-dose (0 h) | 15 min (±5 min) | 30 min (±5 min) | 1 h (±10 min) | 1:30 h (±10 min) | 2 h (±10 min) | 2:30 h (±15 min) | 3 h (±15 min) | 4 h (±30 min) | 6 h (±30 min) | 8 h (±30 min) | 12 h (±30 min) | 24 h (±30 min) | | | |
| Informed consent | X | | | | | | | | | | | | | | | | |
| Inclusion/Exclusion criteria | X | X ¹ | | | | | | | | | | | | | | | |
| Randomization | | X | | | | | | | | | | | | | | | |
| Demographic data | X | | | | | | | | | | | | | | | | |
| Medical history | X | X ² | | | | | | | | | | | | | X ² | X ² | |
| Physical examination | X | X | | | | | X | | | | | | | X | X | X | |
| Vital signs ³ | X | X | | | | | X | | | | | | | X | X | X | |
| Laboratory safety assessments ⁴ | X | X | | | | | X | | | | | | | X | X | X | |
| Viral serology ⁵ | X | | | | | | | | | | | | | | | | |
| Drug of abuse and alcohol screen | X | X | | | | | | | | | | | | | | | |
| Pregnancy test (females only) ⁶ | X | X ⁷ | | | | | | | | | | | | | | | |
| ECG | X | X | | | | | X | | | | | | | X | X | X | |
| PK blood sampling | | X ⁷ | X | X | X | X | X | X | X | X | X | X | X | X | | | |
| Concomitant medications | X | X | X | X | X | X | X | X | X | X | X | X | X | X | X | X | |
| Adverse events ⁸ | X ⁹ | X ⁸ | X | X | X | X | X | X | X | X | X | X | X | X | X | X | |

ECG, electrocardiogram; FU-V, Follow-up Visit; h, hour; IMP, investigational medicinal product; min, minutes; PK, pharmacokinetics

[†] Subjects will be discharged at Day 2 and Day 6 after completing their assessments.

¹ Assessment of changes in inclusion/exclusion criteria

² Assessment of changes in the medical history

³ Vital signs include: blood pressure, pulse rate and body temperature

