2.4 Modifications made in the Statistical Analysis Plan

The following modifications have been made to the analyses specified in Protocol v4.0 (13 December 2023)

Screened population:

The definition of the Screened population has been added.

PK Analysis set:

Protocol definition:

PK analysis set are defined as all randomized subjects who received at least one dose of the study drug medication and have at least one valid PK measurement.

SAP definition:

PK analysis set are defined as all randomized subjects who received at least one dose of the study drug medication and have sufficient data to estimate at least one PK parameter. Subjects with major protocol deviations that might have impacted the PK data collection will be excluded from the population.

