3.2 PK Analysis Set

PK analysis set are defined as all randomized subjects who received at least one dose of the study drug medication and have sufficient data to estimate at least one PK parameter. Subjects with major protocol deviations that might have impacted the PK data collection will be excluded from the population.

PK analyses will be based on PK analysis Set.

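### The protocol's 10% timing criterion for PK exclusion is tighter than the permitted sampling window at 11 of 12 post-dose times, and the SAP redefines the PK set without saying whether the criterion still applies

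*Protocol*

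**What the plan says.** Protocol 13.1.5.1 gives a list of subjects who cannot be assessed for PK. One entry is "Excessive deviation between consecutive blood samples collection from scheduled time of sample collection (more than 10% of the time period between consecutive samplings"). It is not among the starred entries. For unstarred entries the "decision to exclude a subject from the statistical or PK analysis must be made before bioanalysis and has to be properly documented".

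The permitted sampling windows are in the schedule of activities, reproduced in SAP 2.3.5. The first four post-dose columns read "15 min (±5 min) | 30 min (±5 min) | 1 h (±10 min) | 1:30 h (±10 min"). The rest are ±10 min at 2 h, ±15 min at 2.5 and 3 h, and ±30 min at 4, 6, 8, 12 and 24 h.

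The protocol's PK set (13.1.1) requires one dose and one valid PK measurement. The exclusion list stands apart from that definition. SAP 2.4 opens with "The following modifications have been made to the analyses specified in Protocol v4.0 (13 December 2023") and itemises two changes: an added Screened population and a new PK set definition. Under SAP 3.2 a subject must "have sufficient data to estimate at least one PK parameter", and subjects with major deviations that may have affected PK data collection are removed. The SAP does not mention the 10% criterion or the list that contains it.

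**The concern.** An exclusion criterion should not catch subjects whose samples were taken as the protocol allows. If the 10% limit is narrower than the window, a site can follow the schedule exactly and still produce subjects listed as unassessable.

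The SAP leaves open which rule governs. If the protocol list still applies, some of the 6 active subjects per dose can drop out of the PK summaries. If it has lapsed, none do on this ground.

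Timing adds to the problem. Exclusions under this criterion must be decided before bioanalysis, yet protocol 11.2 discloses concentrations to the person responsible for PK analysis after each cohort, and cohort 4 is already complete (protocol 13.4, SAP 5.4.6). While the rule's status is open, a decision on who is in the PK set could be taken with concentrations known, which the pre-bioanalysis requirement is there to prevent.

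**Working it through.** **Inputs.** Nominal post-dose times are from SAP 4.6 (15 and 30 min; 1, 1.5, 2, 2.5, 3, 4, 6, 8, 12 and 24 h). Windows are from SAP 2.3.5. The 10% is from protocol 13.1.5.1. The plan gives no figure of its own to reproduce.

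**Main reading: deviation of a sample against the interval since the previous one.** Limit = 0.10 × preceding interval; ratio = window ÷ limit.

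| Time | Preceding interval (min) | 10% limit (min) | Window (± min) | Window ÷ limit |
|---|---|---|---|---|
| 15 min | 15 | 1.5 | 5 | 3.33 |
| 30 min | 15 | 1.5 | 5 | 3.33 |
| 1 h | 30 | 3 | 10 | 3.33 |
| 1.5 h | 30 | 3 | 10 | 3.33 |
| 2 h | 30 | 3 | 10 | 3.33 |
| 2.5 h | 30 | 3 | 15 | 5.00 |
| 3 h | 30 | 3 | 15 | 5.00 |
| 4 h | 60 | 6 | 30 | 5.00 |
| 6 h | 120 | 12 | 30 | 2.50 |
| 8 h | 120 | 12 | 30 | 2.50 |
| 12 h | 240 | 24 | 30 | 1.25 |
| 24 h | 720 | 72 | 30 | 0.42 |

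The window exceeds the limit at 11 of 12 times.

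**Other readings.** The wording does not say which interval is meant, so I tried the alternatives.

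- Interval to the next sample (11 times, since 24 h has none): ratios 3.33, 1.67, 3.33, 3.33, 3.33, 5, 2.5, 2.5, 2.5, 1.25, 0.42. The window exceeds the limit at 10 of 11.
- Larger of the two adjacent intervals: 10 of 12.
- Change in the gap between consecutive samples: the largest permitted change is the sum of the two windows divided by the interval, with dose time fixed. For example, 2.5 to 3 h gives (15 + 15)/30 = 100%, and 8 to 12 h gives (30 + 30)/240 = 25%. In order the values are 33, 67, 50, 67, 67, 83, 100, 75, 50, 50, 25 and 8%. They exceed 10% at 11 of 12 intervals.

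**Populations.** Protocol 14.11 defines a deviation as noncompliance with the protocol or GCP. A sample taken inside its window is not noncompliance with the schedule, so it gives no ground for exclusion under SAP 3.2. The same subject can be unassessable under protocol 13.1.5.1.

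**Illustration only.** The documents give neither timing accuracy nor the number of breaches that excludes a subject. I assumed independent errors over 24 post-dose samples (two PK days), either normal and truncated to the window or uniform across it, and simulated 200,000 subjects. The table shows planned active subjects kept out of 30 (5 cohorts × 6). The first figure uses sample deviation against the preceding interval; the second uses change in gap.

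| Assumed timing error | No breach tolerated | Up to 1 | Up to 4 |
|---|---|---|---|
| SD 0.5 min | 29.7 / 27.9 | 30.0 / 29.9 | 30.0 / 30.0 |
| SD 1 min | 16.4 / 10.0 | 27.0 / 19.6 | 30.0 / 29.8 |
| SD 2 min | 0.7 / 0.2 | 3.8 / 0.9 | 24.8 / 12.3 |
| Uniform over window | 0 / 0 | 0 / 0 | 0 / 0 |

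The result depends almost wholly on the assumptions. It shows that the effect could be anything from nil to total, not what it will be.

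**The case against.** The strongest reply is that the SAP has already replaced the rule. SAP 2.4 sets the old and new PK set definitions side by side, SAP 3.2 has its own exclusion clause, and neither contains a timing threshold. On that view nothing is lost and one clarifying sentence is missing. This may well be the intention. But the 10% criterion was never part of the definition that SAP 2.4 quotes and replaces. It is a separate list, and no text supplied withdraws it.

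Several narrower points stand:

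- SAP section 2 says two organisations "will perform the statistical analyses described in the protocol". That assigns the work; it does not establish that every protocol rule stays in force.
- Protocol 13.3 is not breached yet. Departures "will be described and justified in a protocol amendment and/or in a revised SAP and/or in the final report", so the final report remains open to the sponsor.
- Exclusion may not be automatic. The protocol speaks of a decision to exclude, gives no number of breaches, and in the same section says that data from every subject with a dose of ATL-001 and a valid measurement will be used.
- Protocol 14.11 counts as major a case where someone "fails to adhere to significant protocol requirements affecting entry criteria, administration of study treatment, administration of prohibited medication or withdrawal criteria". Sample timing is not named, but classification is left to agreement between sponsor and CRO, and SAP 5.3.1 refers to a Protocol Deviation Plan that I have not seen. That plan could affect samples taken outside their windows. It does not help with samples taken inside them.
- Protocol 13.1.5.1 defers detail to a PK analyses SAP. If that is a separate document, it was not available and may settle the matter. The SAP supplied does cover PK parameters and analysis (4.6, 5.4.4) and points elsewhere only for PK table shells.

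These points limit what can be said about the consequence. They do not remove the conflict between the criterion and the schedule.

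**Conclusion.** The concern holds and should be fixed. On every adjacent-interval reading, the schedule permits timing that the protocol's PK exclusion criterion does not: at 11 of 12 times on the preceding interval, with windows 1.25 to 5 times the limit, and at 10 of 11, 10 of 12 or 11 of 12 on the alternatives. This follows from the documents alone.

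The number of subjects affected does not. It is zero if SAP 3.2 was meant to replace the list; otherwise it depends on timing accuracy and on the number of breaches tolerated, neither of which is stated. The effect is confined to the secondary PK summaries, which are descriptive. The primary safety analysis is untouched. The documents also do not say that the analysis after cohort 4 included PK; the protocol describes its results as safety and efficacy.

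**What to change.** In SAP 2.4 and 3.2, state that the 10% subject-level criterion of protocol 13.1.5.1 is withdrawn, and give the justification that protocol 13.3 calls for. The alternative is to keep a timing criterion, set it to the schedule windows, and apply it to the individual sample rather than the whole subject.

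Whichever is chosen, use the same rule for all five cohorts, put it in writing before subjects are allocated to the PK set, and document whether any subject in cohorts 1 to 4 was excluded under the present wording.

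A related clarification, unless a separate PK SAP already covers it: say that the non-compartmental analysis uses actual elapsed times. SAP 5.4.4 mentions nominal time only for the concentration summaries.

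The cost is a few SAP sentences and one check of existing records. Sampling, sample size and the safety analysis do not change.
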